2 STUDY OVERVIEW

2.1 Study Objectives

2.1.1 Primary Study Objective(s)

To evaluate the safety and tolerability of MEDI8897 compared to palivizumab when administered to preterm infants entering their first RSV season and children with CLD or CHD entering their first and second RSV season.

2.1.2 Secondary Study Objectives

- 1 To evaluate serum concentrations of MEDI8897 and palivizumab
- 2 To evaluate ADA responses to MEDI8897 and to palivizumab in serum
- To assess the descriptive efficacy of MEDI8897 when administered as a single IM dose of 50 mg to infants < 5 kg or 100 mg to infants ≥ 5 kg in the first RSV season or a single 200 mg IM dose administered in the second RSV season, in reducing medically attended LRTI (inpatient and outpatient) and hospitalization due to RT-PCR-confirmed RSV, compared to palivizumab.

2.1.3 Exploratory Study Objectives

- 4 To assess HRU and caregiver burden for MEDI8897 recipients compared to palivizumab recipients
- To determine anti-RSV neutralizing antibody levels in serum afforded by a single dose of MEDI8897 compared to 5 monthly doses of palivizumab
- To evaluate exposure to RSV by measuring seroresponses to different RSV proteins in MEDI8897 and palivizumab recipients and to evaluate the levels of maternal RSV-specific antibody in MEDI8897 and palivizumab recipients

- 7 To characterize resistance to MEDI8897 through genotypic and phenotypic analyses
- 8 To assess the incidence of medically attended LRTI due to RT-PCR-confirmed RSV, compared to palivizumab after Day 151 (between Day 152 and Day 361)

2.2 Study Design

This is a randomized, double-blind, palivizumab-controlled study in which approximately 900 palivizumab-eligible infants entering their first RSV season will be enrolled into one of 2 cohorts (Figure 1): (1) preterm cohort, including approximately 600 preterm infants (\leq 35 weeks gestational age [GA]) without CLD/CHD, or (2) CLD/CHD cohort, including approximately 300 infants with CLD of prematurity or hemodynamically significant CHD. A minimum of 100 infants with hemodynamically significant CHD will be enrolled. Within each cohort, randomization will be stratified by hemisphere (northern, southern) and subject age at the time of Season 1 randomization (\leq 3.0 months, > 3.0 to \leq 6.0 months, > 6.0 months).

Season 1, Preterm and CLD/CHD Cohorts

All subjects will be randomized 2:1 to either the MEDI8897 group (approximately 600 subjects, including approximately 400 subjects in the preterm cohort and approximately 200 subjects in the CLD/CHD cohort) or palivizumab group (approximately 300 subjects, including approximately 200 subjects in the preterm cohort and 100 subjects in the CLD/CHD cohort). Subjects in the MEDI8897 group will receive a single fixed IM dose of MEDI8897 followed by 4 once-monthly IM doses of placebo. The MEDI8897 dose level will be stratified by weight band, ie, 50 mg for infants weighing < 5 kg or 100 mg for infants weighing \ge 5 kg. Subjects in the palivizumab group will receive 5 once-monthly IM doses of 15 mg/kg palivizumab.

Season 2, CLD/CHD Cohort Only

[figure not shown]
- Subjects with CLD/CHD ≤ 24 months of age who were randomized to the MEDI8897 group for Season 1 will receive a single fixed IM dose of 200 mg MEDI8897 followed by 4 once-monthly IM doses of placebo (approximately 200 subjects).
- Subjects with CLD/CHD ≤ 24 months of age who were randomized to the palivizumab group for Season 1 will be re randomized 1:1 to either the MEDI8897 group or the palivizumab group. Subjects in the MEDI8897 group will receive a single fixed IM dose of 200 mg MEDI8897 followed by 4 once monthly IM doses of placebo (approximately 50 subjects). Subjects in the palivizumab group will receive 5 once monthly IM doses of 15 mg/kg palivizumab (approximately 50 subjects).

In Season 1 or Season 2, subjects in the CLD/CHD cohort who undergo cardiac surgery with cardiopulmonary bypass after receipt of Dose 1 but prior to receipt of Dose 5 will receive a replacement dose of the study drug they received for Dose 1 immediately following the

surgery when determined by the physician to be medically stable for an IM injection. Any subsequent doses of study drug will continue to be given according to the protocol specified dosing schedule.

Subjects in the preterm cohort will be followed through 1 year after Season 1/Dose 1, and subjects in the CLD/CHD cohort will be followed through 1 year after Season 2/Dose 1. Subjects in the CLD/CHD cohort who receive a replacement dose in Season 2 will be followed through 1 year after the last replacement dose.

Figure 1: Study Design

2.3 Treatment Assignment and Blinding

2.3.1 Methods for Assigning Treatment Groups

An IWRS will be used for randomization to a treatment group and assignment of blinded investigational product kit numbers. A subject is considered randomized into the study when the investigator notifies the IWRS that the subject meets eligibility criteria and the IWRS provides the assignment of blinded investigational product kit numbers to the subject.

In Season 1, subjects in the preterm and CLD/CHD cohorts will be randomized using a 2:1 ratio to either the MEDI8897 group or palivizumab group. Within each cohort, the randomization will be stratified by hemisphere (northern, southern) and subject age at the time of Season 1 randomization ($\leq 3.0 \text{ months}$, $> 3.0 \text{ to} \leq 6.0 \text{ months}$, > 6.0 months).

In Season 2, subjects in the CLD/CHD cohort only will be randomized. Subjects who were randomized to the MEDI8897 group in Season 1 will remain in the MEDI8897 group. Subjects who were randomized to the palivizumab group in Season 1 will be re-randomized using a 1:1 ratio to either the MEDI8897 or palivizumab group. For simplicity, the following notations will be used to describe the treatment groups in Season 2.

- MEDI8897/MEDI8897: CHD/CLD subjects who were randomized to MEDI8897 group in Season 1 and remained in MEDI8897 group in Season 2.
- Palivizumab/MEDI8897: CHD/CLD subjects who were randomized to Palivizumab group in Season 1 and re-randomized to MEDI8897 group in Season 2.
- Palivizumab/Palivizumab: CHD/CLD subjects who were randomized to Palivizumab group in Season 1 and re-randomized to Palivizumab group in Season 2.

Study drug (MEDI8897, placebo, or palivizumab) must be administered the same day the study drug is assigned. If there is a delay in the administration of study drug such that it will not be administered within the specified timeframe, the unblinded investigational product monitor must be notified immediately.

2.3.2 Methods to Ensure Blinding

This is a double-blind study in which MedImmune will provide sites with MEDI8897 and palivizumab. Sites will use commercially available saline as the placebo. Syringe barrels will be covered by the unblinded investigational product manager. Neither the subject/legal representative nor the investigator or any of the site staff who are involved in the treatment or clinical evaluation of the subjects will be aware of the treatment received (ICH E9). In the event that treatment allocation for a subject becomes known to the investigator or other

blinded study staff involved in the management of study subjects, the sponsor must be notified *immediately*. If the treatment allocation for a subject needs to be known to treat an individual subject for an AE, the investigator must notify the sponsor *immediately*. The site will maintain a written plan detailing which staff members are blinded/unblinded and the process of investigational product administration used to maintain the blind.

2.3.3 Methods for Unblinding

2.3.3.1 Unblinding in the Event of a Medical Emergency

In the event of a medical emergency, the investigator may unblind an individual subject's investigational product allocation. Instructions for unblinding an individual subject's study drug allocation are contained in the IWRS manual. In general, unblinding should only occur if management of the medical emergency would be different based on the subject having received study drug. In the majority of cases, the management of a medical emergency would be the same whether or not study drug was received by the subject. If this was the case, the study drug allocation should not be unblinded. In the event there is unblinding, the investigator should promptly document and explain to MedImmune the reason for any premature unblinding.

MedImmune retains the right to unblind the treatment allocation for SAEs that are unexpected and are suspected to be causally related to a study drug and that potentially require expedited reporting to regulatory authorities.

If a subject's study drug allocation is unblinded to the blinded staff or blinded MedImmune/contract research organization study team, the subject should be discontinued from study drug.

Site personnel and parents/guardians of the subjects will remain blinded to the treatment assignment until the end of the study.

2.4 Sample Size

With respect to safety, 600 subjects exposed to MEDI8897 in Season 1 will provide a 95% probability of observing at least one AE if the true event rate is 0.5%; if no AEs are observed, this study provides 95% confidence that the true event rate is < 0.5%. The sample size is for safety consideration.

With respect to the descriptive efficacy, 600 subjects will be exposed to MEDI8897 and 300 subjects will be exposed to palivizumab in Season 1 to observe numerically similar efficacy for both mAbs. Using an assumption of a 6% medically attended RSV LRTI rate in palivizumab recipients, approximately 18 events will be observed in that group. The 6% RSV

LRTI rate (1.9% RSV hospitalizations and 3.9% outpatient RSV illness) was based on a prior study in preterm infants with and without CLD who received palivizumab (Carbonell-Estrany X, 2010). Assuming a 6% rate of medically attended RSV LRTI in MEDI8897 recipients, 600 MEDI8897 subjects in Season 1 will provide approximately 36 events in that group. However, because of the largely reduced RSV circulation due to COVID-19 pandemic related measures, the observed event rates could be much lower.

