4.8.2 Sample Size

With respect to safety, 600 subjects exposed to MEDI8897 in Season 1 will provide a 95% probability of observing at least one AE if the true event rate is 0.5%; if no AEs are observed, this study provides 95% confidence that the true event rate is $< 0.5\%$. The sample size is for safety consideration.

With respect to efficacy, approximately 600 subjects will be exposed to MEDI8897 and 300 subjects will be exposed to palivizumab in Season 1 to observe numerically similar efficacy for both mAbs. Because of the reduced incidence of RSV disease in this population following the introduction of palivizumab, a superiority or non-inferiority design is not practical. A valid non-inferiority margin cannot be established due to the lack of historical efficacy data for the medically attended RSV LRTI endpoint for palivizumab. Therefore, there is no hypothesis testing for efficacy. Using an assumption of a 6% RSV LRTI rate in palivizumab recipients, approximately 18 events will be observed in that group. The 6% RSV LRTI rate (1.9% RSV hospitalizations and 3.9% outpatient RSV illness) was based on a prior study in preterm infants with and without CLD who received palivizumab (Carbonell-Estrany et al, 2010). Assuming a 6% rate of RSV LRTI in MEDI8897 recipients, 600 MEDI8897 subjects in Season 1 will provide approximately 36 events in that group. However, because of the largely reduced RSV circulation due to COVID-19 pandemic-related measures, the observed event rates could be much lower. Only summaries will be provided for efficacy unless specified otherwise.

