3.5.1 Incidence of medically attended LRTI due to RT-PCR-confirmed RSV

The determination of medically attended RSV LRTI will be based on objective clinical LRTI criteria (described in the Protocol Section 4.3.1.1 and SAP Appendix 1) and RSV test results obtained from analyzing the respiratory secretions using a validated RSV RT-PCR assay for the detection of RSV A or RSV B performed in a central laboratory. These LRTI events may occur in the inpatient or outpatient visit setting.

Based on a blinded review of data, it is determined that a medically attended LRTI will be counted as a medically attended RSV LRTI if there is a respiratory sample tested RSV positive and collected within [-7, 14] days relative to the initial date seen by the healthcare provider (eg, admission/deterioration date associated with the event, urgent care visit, outpatient emergency department [ED] visit, or outpatient clinic visit). In addition, deaths that can be demonstrated as caused by RSV (by autopsy or clinical history and virologic evidence) will also be considered as primary medically attended RSV LRTI events.

3.5.1.1 Analysis of incidence of medically attended LRTI due to RT-PCR-confirmed RSV in Season 1

The incidence of medically attended RSV LRTI (inpatient and outpatient) through 150 days post 1st dose (ie, during a typical 5-month RSV season) in Season 1 is the primary efficacy endpoint and will be summarized by treatment group as well as for all subjects using ITT

population. The 95% Clopper-Pearson (exact) confidence interval of the incidence rate for each treatment group will be produced using the SAS Procedure PROC FREQ with the EXACT statement. For subjects with multiple medically attended RSV LRTI events, only the first occurrence will be used in the summary. Summary of the incidence of medically attended RSV LRTI will also be repeated for CHD subjects and CLD subjects separately.

In addition, the incidence of medically attended RSV LRTI will be further tabulated by Inpatient (primary hospitalization, nosocomial hospitalization) and Outpatient, for the latter category, further presentation will be made by different medical settings: outpatient clinic, urgent care clinic, and ED visits for subjects who did not have a hospitalization due to RSV.

The incidence of medically attended RSV LRTI will also be summarized by the following subgroups:

- Hemisphere
- Age at randomization stratum (age \leq 3.0 months, age > 3.0 to \leq 6.0 months, age > 6.0 months)

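### Comparative objectives in a 2:1 randomised trial, but no Season 1 between-arm estimate or interval is pre-specified for safety or efficacy

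*SAP*

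**What the plan says.** The aims are comparative. SAP 2.1.1 gives the primary objective as "To evaluate the safety and tolerability of MEDI8897 compared to palivizumab", and Protocol Table 1 agrees. The efficacy objective (SAP 2.1.2, Protocol Table 2) is to reduce RSV LRTI and RSV hospitalization relative to palivizumab. Protocol 3.2.3 describes the safety endpoint as a comparison of the two profiles. The design supports this: "All subjects will be randomized 2:1" (SAP 2.2), stratified within cohort by hemisphere and age.

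On sizing, SAP 2.4 states that "600 subjects exposed to MEDI8897 in Season 1 will provide a 95% probability of observing at least one AE" at a true rate of 0.5%, and then that "The sample size is for safety consideration". It goes on to say that 300 "subjects will be exposed to palivizumab in Season 1 to observe numerically similar efficacy for both mAbs". Protocol 4.8.2 says nearly the same and adds "Only summaries will be provided for efficacy unless specified otherwise".

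On analysis, SAP 3.5.1.1 says a 95% Clopper-Pearson "confidence interval of the incidence rate for each treatment group will be produced using the SAS Procedure PROC FREQ with the EXACT statement". SAP 3.5.2 summarises RSV hospitalization by arm. SAP 3.7 summarises adverse events by arm as counts and percentages. SAP 1 rules out formal testing for both safety and efficacy. The SAP abbreviation list includes relative risk and Cochran-Mantel-Haenszel, but no analysis in the SAP uses either.

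**The concern.** A descriptive trial needs no hypothesis test. It does need an estimate of the quantity its objectives name, with the uncertainty in that estimate. Here that quantity is the contrast between arms, and the plan stops one step short of it.

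Readers of the report will compare the arms anyway, by eye or by checking whether the two separate intervals overlap. Overlap does not measure the uncertainty in a difference, because intervals can overlap when the interval for the difference excludes zero. With few events, a chance imbalance can look like a real difference, and wide uncertainty can look like similarity. Any contrast added later would be computed by a method chosen after the data were seen. This matters most for safety, which is the primary objective and is assessed directly in this trial.

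**Working it through.** **1. The plan's own figures.** From SAP 2.4: 600 exposed, true rate 0.5%.
- P(at least one event) = 1 - 0.995^600 = 0.951. Stated: 95%.
- One-sided 95% upper bound with no events = 1 - 0.05^(1/600) = 0.498%. Stated: below 0.5%.
- Expected RSV LRTI events at 6%: 600 x 0.06 = 36 and 300 x 0.06 = 18, as stated.

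All reproduce. The sizing arithmetic is not in question.

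**2. What the planned intervals show at 6%.** Clopper-Pearson: 36/600 gives 4.2% to 8.2%; 18/300 gives 3.6% to 9.3%. Neither describes the difference.

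**3. The missing contrast at 6%.**
- Newcombe difference. Wilson limits are 4.37% to 8.19% (36/600) and 3.83% to 9.28% (18/300). Lower limit = 0 - sqrt((6.00 - 4.37)^2 + (9.28 - 6.00)^2) = -3.7 points. Upper limit = 0 + sqrt((8.19 - 6.00)^2 + (6.00 - 3.83)^2) = +3.1 points.
- Risk ratio. SE(log RR) = sqrt(1/36 - 1/600 + 1/18 - 1/300) = 0.280; exp(±1.96 x 0.280) = 0.58 to 1.73.

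**4. Lower rates.** SAP 2.4 warns that rates could be much lower but gives no figure. The 2% and 1% rows are assumptions.

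| Rate in both arms | Events | Difference, 95% CI (points) | RR, 95% CI |
|---|---|---|---|
| 6% (documents) | 36 and 18 | -3.7 to +3.1 | 0.58 to 1.73 |
| 2% (assumed) | 12 and 6 | -2.4 to +1.8 | 0.38 to 2.64 |
| 1% (assumed) | 6 and 3 | -2.0 to +1.3 | 0.25 to 3.97 |

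With equal true rates, exact binomial calculation puts the observed ratio outside 2/3 to 1.5 in 15% of trials at 6% and 40% at 2%. At 1% it is 49%, plus a further 5% of trials with no palivizumab events, where the ratio cannot be computed.

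**5. Why overlap misleads.** Take an illustrative 36/600 against 30/300. The planned per-arm intervals, 4.2% to 8.2% and 6.8% to 14.0%, overlap. The Newcombe interval for the difference of -4.0 points is -8.2 to -0.4, which excludes zero.

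**6. Safety.** Protocol 1.4.1 reports TESAEs in 10.4% of MEDI8897 subjects in the Phase 2b study. If that rate applied to both arms here (an assumption, since that study enrolled healthy preterm infants), the half-width of the difference would be 1.96 x sqrt(0.104 x 0.896 x (1/600 + 1/300)) = 4.2 points. For a category with no events in either arm, the Newcombe interval is -1.3 to +0.6 points.

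**7. Stratification.** Two cohorts x two hemispheres x three age groups = 12 strata. At 1%, the 6 + 3 = 9 expected events are fewer than the strata.

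**The case against.** The strongest reply is that the study is openly descriptive. Protocol 4.8.2 explains why superiority and non-inferiority designs are impractical and why no valid margin exists. Efficacy is to be supported by extrapolation from the Phase 2b and Phase 3 studies (SAP 1 and 3.9, Protocol 3.2.3), under a separate plan not available here. Side-by-side randomised arms meet the comparative wording in a descriptive sense, and anyone can derive a crude difference from the reported counts. For Season 2 the SAP itself cautions against direct comparison with the group given MEDI8897 in both seasons.

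Much of this stands. It lowers the stakes for efficacy, and no rule in the documents is broken. But the stated reasons justify omitting a test and a margin. They do not explain omitting an estimate and its interval. The Season 2 caution rests on possible dropout bias and does not extend to Season 1, where the randomised contrast is cleanest. Extrapolation does not remove the need for a direct safety comparison.

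A reader might infer two stronger things: that the trial was sized to demonstrate similar efficacy, and that the plan will claim similarity it cannot support. The documents support neither. SAP 2.4 assigns the sample size to safety just before the efficacy phrase, and no section proposes to conclude similarity from this trial.

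**Conclusion.** The point holds as an analysis gap plus loose wording. The objectives are comparative and the arms are randomised, but no between-arm estimate or interval is specified for safety or efficacy. The phrase about numerical similarity has no criterion attached. The sample size is correctly stated and needs no change.

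The size of the gap is the uncertainty left unreported: about 3 to 4 points either side of zero, or a ratio interval of 0.58 to 1.73, at the documents' 6%. The ratio interval widens further at lower rates. These figures assume full enrolment of 600 and 300, equal true rates and no stratification. Reporting the interval would show this uncertainty; it would not establish similarity. The change is a worthwhile low-cost improvement, with more weight for safety than for efficacy.

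**What to change.** In SAP 3.5 and 3.7, pre-specify for Season 1 a descriptive MEDI8897 minus palivizumab risk difference with a 95% interval. Apply it to any TEAE, TESAE, AESI, NOCD, medically attended RSV LRTI and RSV hospitalization. Name one method, Miettinen-Nurminen or Newcombe, either unstratified or stratified by cohort only, because 12 strata are too sparse. State that no p-value or margin applies.

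In SAP 2.4 and Protocol 4.8.2, replace the phrase about numerical similarity with the expected precision in the table above, labelling the 2% and 1% rates as assumptions.

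The cost is one extra column in existing tables and a few lines of text. Sample size, data collection and conduct are unaffected. The downside for the sponsor is that the wide intervals become visible.

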3 STATISTICAL METHODS

3.1 General Considerations

There are 3 planned analyses for this study: the primary analysis, the Season 2 analysis and the final analysis. The primary analysis will be conducted after all randomized subjects have completed follow-up through the first 5-month RSV season (ie, Season 1 Day 151 visit) and include all available Season 1 safety, efficacy, PK, and ADA data at the time of the data cutoff. The Season 2 analysis will be conducted after all CLD/CHD subjects have completed follow-up through the second 5-month RSV season (ie, Season 2 Day 151 visit) and include all available Season 1 data and Season 2 safety, efficacy, PK, and ADA data at the time of the data cutoff. The final analysis will be conducted when all subjects have completed the last visit of the study and include all data collected in the study.

At the time of the primary analysis, the Season 1 data will be unblinded to Sponsor/designated clinical research organization associated with the analysis, write-up and submission. To ensure the blinding of Season 2 treatment assignment for CHD/CLD subjects who were randomized to palivizumab arm in Season 1, any data with potential unblinding risk will be split by Season 1 and Season 2 by the corresponding third party data vendors and when the primary database lock (DBL) occurs, only unblinding data from Season 1 will be transferred to the Sponsor for analysis.

The site personnel, participants, and the study team members who participate in the advice or decisions involving study subjects and/or day-to-day interactions with the site, will remain blinded until the end of the study to ensure the trial integrity is maintained. Details of the unblinding process will be documented in a separated file of unblinding plan.

For the visit-based summaries for ADA, RSV neutralizing antibody, RSV serology, and clinical laboratory data, the summaries will be based on the scheduled days with adjusted analysis-defined visit windows. The adjusted analysis-defined windows will be based on the collection schedule listed in the protocol and summaries will be windowed to the closest scheduled visit for those data. Visit windows have been constructed so that every observation collected can be allocated to a particular visit. However, all data will be included in the listings. If multiple readings are recorded within a single analysis-defined visit window, the following rules will apply:

- If there are 2 or more valid, non-missing observations within the same visit window, and
 - if they are on different days, then the non-missing one which is closest to the scheduled visit day will be used in the analysis.
 - if they are on the same day which is closest to the scheduled visit day, then the non-missing one with the later collection time will be used in the analysis.
- If 2 or more valid observations are equidistant from the scheduled visit, and
 - if they are on different days, then the non-missing observation with the earlier collection date will be used in the analysis for the post-baseline observations, and the non-missing observation with the later collection date will be used in the analysis for the screening observations.
 - if they are on the same day, then the non-missing observation with the later collection time will be used in the analysis.
- For LRTI visits or unscheduled visits, if 2 or more valid observations are collected on the same day, then the non-missing observation with the earlier collection time will be included in the analysis.
- If a visit window does not contain any observations, then the data will remain missing.
- For the visit-based summaries for ADA, if both ADA positive and negative samples are available within a subject's visit, ADA positive will be reported.

For assignment of data to adjusted analysis-defined visit windows, study day will be defined as:

- Screening period: Study day = Date of assessment date of randomization
- After randomization: Study day = Date of assessment date of randomization + 1

The adjusted analysis-defined windows for ADA, RSV neutralizing antibody, and RSV serology are defined in Appendix 2, and for clinical laboratory data are defined in Appendix 3.

The partial dates imputation rules are described in Appendix 4 and Appendix 5.

Categorical data will be summarized by the number and percentage of subjects in each category. Continuous variables will be summarized by mean, median, standard deviation, minimum, and maximum. In general, unless stated otherwise, baseline of each season will be defined as the last non-missing value within 30 days prior to the 1st dosing of the season. Baseline of Season 1 + Season 2 will be the same as baseline of Season 1.Data analyses will be conducted using the SAS® System Version 9.4 or higher (SAS Institute Inc., Cary, NC).

